**5.4 SCREEN FAILURES**

If a participant who consents to participate in this study but is deemed ineligible via a screening assessment (PARQ+, Eligibility Questionnaire) will not have identifying information recorded. Only the reason for ineligibility will be recorded. Responses to the PARQ+ or eligibility questionnaire will be destroyed. Individuals who do not meet the criteria for participation in this trial will not be rescreened.

## 5.5 STRATEGIES FOR RECRUITMENT AND RETENTION

We seek to recruit 20 individuals per phase, 10 of which will be female and 10 of which will be male. Participants will be recruited from the community in Guelph, Ontario. In line with our IRB approved methods, recruitment posters will be posted at the University of Guelph and around the city. A social media posting will be sent via Twitter from the official Human Performance and Health Research Laboratory account. Additionally, the study poster will be presented to students in undergraduate lectures at the University of Guelph. Participants may also be recruited by word of mouth. Each participant who completes a session of microneurography will be compensated \$100 CAD in line with typical institutional procedures.

## 6 STUDY INTERVENTION

### 6.1 STUDY INTERVENTION(S) ADMINISTRATION

#### 6.1.1 STUDY INTERVENTION DESCRIPTION

The two cannabis strains examined in the current study are Rex and Kalea (See accompanying Investigator's Brochure). These cannabis strains will be given in the form of dried cannabis flower. Each of these cannabis strains are produced by MedReLeaf. Both Rex and Kalea are harvested from *Cannabis sativa*. These strains have been selected as they differ substantially in their concentration of the two most abundant cannabinoids THC and CBD. Rex will contain  $13.6 \pm 2.7\%$  THC and  $<1\%$  CBD by dry weight; Kalea will contain  $<1\%$  THC and  $14.5 \pm 2.9\%$  CBD by dry weight. For more detail about the investigational products please see the accompanying Investigator's Brochures.

#### 6.1.2 DOSING AND ADMINISTRATION

All cannabis consumed in relation to the current study will be done so during a study visit, within a laboratory setting in a specifically designed cannabis administration chamber. Participants will not be required to consume cannabis for the purpose of the study outside of their visits to the laboratory.

In each study visit a standard dosage of 100mg of Rex or Kalea will be administered to participants, who will consume via inhalation of smoke or vapor. Participants will be seated in a chamber designated for cannabis consumption. One investigator will retrieve a pre-weighed 100mg dose of the appropriate dried cannabis flower, depending on the phase of study, and the study visit being completed. The investigator will load the 100mg cannabis dose into either a glass smoking apparatus or a "Mighty Medic" vaporizer. The vaporizer or smoking apparatus will be given to the participant within the cannabis chamber.

Cannabis will be inhaled according to a standardized inhalation procedure. This procedure involves 5 seconds of inhalation, 10 seconds wherein smoke or vapor is held in, and 45

seconds of rest. This procedure will be repeated until all cannabis has been exhausted. After receiving the full dose of cannabis, an investigator will guide the participant out of the chamber.

## 6.2 PREPARATION/HANDLING/STORAGE/ACCOUNTABILITY

### 6.2.1 ACQUISITION AND ACCOUNTABILITY

Aurora Cannabis Inc. will provide the exact amounts of Rex and Kalea needed for the completion of the study by 20 individuals. As the required sample size has been determined to be 20 individuals, with each participant consuming 100mg of cannabis on four separate occasions, per phase of study, 12 grams of Rex and 4 grams of Kalea will be required. An additional 3 grams of Rex and an extra gram of Kalea will be purchased to account for the potential of participant drop-out. Cannabis will be stored in a locked safe in a room with restricted access. Only members of the investigatory team will have access to the room where the cannabis is stored, and the room will not be accessed alone by any researcher. The safe will be secured to the wall of the room. Each entry to the room for the access of cannabis will be recorded in a log, where time of exit and entry, and purpose of entry will be recorded. Additionally, all cannabis will be immediately inventoried upon receipt, and a constant record will be kept of how much cannabis is removed at any time. Cannabis will be organized into pre-weighed 100mg samples, and will be labelled by sample number. Any time cannabis is removed, the responsible individual will be required to record what sample was removed. Weekly checks of cannabis inventory will be performed. Any excess cannabis that remains at the end of the data collection period will be destroyed. Cannabis will be ground and mixed with equal parts soil before being discarded.

### 6.2.2 FORMULATION, APPEARANCE, PACKAGING, AND LABELING

Please see the investigator's brochure for information related to formulation, appearance, packaging, and labeling. Each brochure was prepared by MedReLeaf, a subsidiary of Aurora Cannabis Inc.

### 6.2.3 PRODUCT STORAGE AND STABILITY

Each strain of cannabis will be stored locked safe in a room with restricted access. Samples will be stored in 100mg preparations.

### 6.2.4 PREPARATION

Prior to receiving any cannabis, the investigatory team will label and prepare child resistant jars that will contain individual 100mg dosages. Each container will be labelled with a sample number for tracking purposes. These containers will be kept in the safe. Upon receiving a shipment of cannabis, an investigator will transport the cannabis to the room for storage. They will then pre-weigh 100mg samples using a digital scale, and place a 100mg dose of dried cannabis flower into each container. A master list of which strain each sample number corresponds to will be kept.

At the point in each study visit where the participant is prepared for cannabis consumption, two members of the research team will retrieve the appropriate cannabis sample from the safe. The sample will be loaded into the appropriate inhalation device within the restricted access room.

The smoking apparatus will be prepared by placing the entirety of one dose into the bowl portion of the glass smoking apparatus. The device will then be given to the participant to begin the inhalation protocol.

The Mighty Medic vaporizer will be loaded according to the manufacturer's instructions. The cooling unit will be rotated 90° in the counterclockwise direction. One dose will then be placed in the now exposed filling chamber. The cooling unit will be moved to the initial position, and the vaporizer will be set to a temperature of 190°C and given to the participant to begin the inhalation protocol.

### 6.3 MEASURES TO MINIMIZE BIAS: RANDOMIZATION AND BLINDING

As the current study utilizes a randomized crossover (within subject) design, no randomization to independent groups is necessary. Instead, the order in which experimental study visits take place will be randomized, and individualized to each participant. Upon enrollment in the study, the individualized order of study visits will be determined using a random number generating software (<https://www.random.org>). Each study visit will be assigned a number from 1-4. Random numbers will be generated, and the order of study visits will correspond to the order in which the numbers were generated by the software.

*Phase I* of this study will not be blinded owing to challenges in masking the device used to inhale cannabis. *Phase II* will be single blinded, with the strain of cannabis consumed unbeknownst to the participant. Participants will not be unblinded to the study conditions at any point. All investigators will however be blind to condition during data analysis.

Primary and secondary endpoints used in this study are robust in preventing observer bias. Each primary endpoint will be determined using computer software, while secondary endpoints will also be determined by the use of automatic devices that provide data that is not modifiable by investigators. During any analysis, the investigator will be blinded to condition

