**1 PROTOCOL SUMMARY****1.1 SYNOPSIS**

Title:	The Influence of Cannabis Inhalation During Exercise on Cardiovascular Health and Function: Exploring the Balance of Cannabinoids and Mode of Administration to Decrease Risk and Maximize Benefits
Study Description:	The current study will examine the acute cardiovascular response to cannabis consumption at rest, and when combined with exercise. It will examine the influence of inhalation method, and cannabinoid concentration.
Objectives:	
Primary Objective: Determine the effects of cannabis consumption at rest and during exercise on the human cardiovascular system
 
Secondary Objective: investigate the influence of consumption methods (smoking vs. vaporizing) and cannabinoid balances (i.e. THC vs. CBD). Determine the effects of cannabis consumption on exercise performance

Endpoints:	
Primary Endpoints: Carotid-Femoral Pulse Wave Velocity, Brachial Artery Flow-Mediated Dilation, Cardiac Function (dynamics), Muscle Sympathetic Nerve Activity
 
Secondary Endpoints: Blood Pressure, Heart Rate, Work Completed, Rate Pressure Product, Rating of Perceived Exertion

Study Population:	20, healthy male and female recreational cannabis users aged 19-45yr will be recruited for the current study
Description of Sites/Facilities Enrolling Participants:	All activities will be performed at the Human Performance and Health Research Laboratory in the Department of Human Health and Nutritional Sciences, College of Biological Sciences, at the University of Guelph. All research will be conducted in Guelph, Ontario, Canada. Participants will healthy volunteers.

**Description of Study Intervention:** Participants will consume 100mg of cannabis via smoking or vaporizing. Cannabis consumed will possess THC and CBD ratios of either  $13.6 \pm 2.7\% : <1\%$ , or  $<1\% : 14.5 \pm 2.9\%$ .

**Study Duration:** It is estimated that the current study will require a 12 month period for completion, beginning from the onset of study enrollment, to the completion of data analysis

[figure not shown]
**Participant Duration:** Depending on degree of involvement, participant duration of this study will be either 6 weeks, or 10 weeks.

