### 1.3 SCHEDULE OF ACTIVITIES (SOA)

Procedure	Introductory Visit (Visit 0), Day 0	Exercise Control Visit (Visit 1), Day 7±1 day	Phase I Cannabis Visit (Visit 2), Day 14±1 day	Phase I Cannabis + Exercise Visit (Visit 3), Day 21±1 day	Phase I Cannabis Visit (Visit 4), Day 28±1 day	Phase I Cannabis + Exercise Visit (Visit 5), Day 35±1 day	Phase II Cannabis Visit (Visit 6), Day 42±1 day	Phase II Cannabis + Exercise Visit (Visit 7), Day 49±1 day	Phase II Cannabis Visit (Visit 8), Day 56±1 day	Phase II Cannabis + Exercise Visit (Visit 9), Day 63±1 day
Informed Consent	X									
Eligibility Questionnaire	X									
Physical Activity Readiness Questionnaire	X									
Height	X									
Weight	X	X	X	X	X	X	X	X	X	X
Blood Pressure and Heart Rate	X	X	X	X	X	X	X	X	X	X
Urine Test	X	X	X	X	X	X	X	X	X	X
Inquiry of Changes to Health and Prescription Status		X	X	X	X	X	X	X	X	X
VO 2 Max Test	X									
Pulse Wave Velocity		X	X	X	X	X	X	X	X	X
Brachial Artery FMD		X	X	X	X	X	X	X	X	X
Echocardiography		X	X	X	X	X	X	X	X	X
20 Minute Maximal Cycling Exercise		X		X		X		X		X
Vaporization of High THC Cannabis			X	X				X	X	
Smoking of High THC Cannabis					X	X				
Vaporization of High CBD Cannabis							X			X
Indirect Calorimetry/CPET	X	X		X		X		X		X
Microneurography (MSNA)			X							
Stress Echocardiography			X		X		X		X	
Measurement of Continuous Blood Pressure		X	X	X	X	X	X	X	X	X
ECG	X	X	X	X	X	X	X	X	X	X
Impedance Cardiography		X		X		X		X		X
Drug Effects Questionnaire			X	X	X	X	X	X	X	X

*This study will use a randomized crossover design. Phase I of this study will occur prior to the initiation of phase II. If a participant enters the study in phase II, but did not participate in phase I, they will be required to complete the introductory and exercise control visits. Visits 2-5 and 6-9 will occur in a randomized order, which will be individualized for each participant.*

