## 4 STUDY DESIGN

### 4.1 OVERALL DESIGN

The study will use a randomized cross-over design. It will be structured by division into two phases. Both phases will examine the acute cardiovascular response to cannabis consumption,

both at rest and during exercise. *Phase I* will examine if and how this response differs whether cannabis is smoked or vaporized. *Phase II* will examine how this response is influenced by cannabinoid concentration within inhaled cannabis. Phase II of the current study will use a single-blind design, with participants being unaware of the relative cannabinoid concentrations of the cannabis they consume. Cannabis will be inhaled using methods of smoking (phase I only) or vaporization (phase I and II). Each experimental study visit (study visits 2-9), 100mg of cannabis will be consumed via one of the two aforementioned methods of inhalation, followed by a subsequent rest period, or by 20 minutes of exercise. Primary endpoints will be examined pre- and post-consumption each visit (with the exception of muscle sympathetic nerve activity, which will only be performed on a single study visit), while secondary endpoints will be recorded during exercise.

Each phase of the study will require participants to complete an introductory and control visit, as well as 4 experimental study visits, where cannabis inhaled under alternating conditions (phase I: smoking vs. vaporizing high THC cannabis, phase II: high CBD cannabis vs. high THC cannabis) followed by exercise, or a time-matched rest period. The order in which these visits will occur will be randomized, and individualized for each participant. A within-subjects design will be utilized, so that each participant completes each condition. High THC cannabis used will be the cannabis strain “Rex”, while the high CBD strain will be “Kalea”. The dose size and strength will not be altered throughout the course of the study.

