## 4.2 SCIENTIFIC RATIONALE FOR STUDY DESIGN

A within subject design has been chosen for this study due to potential variability in primary endpoints between individuals. Specifically, variation in pulse wave velocity and flow-mediated dilation. Published reference values for pulse wave velocity in our selected age group may range between 3.92m/s and 8.26m/s. This substantial range requires a within-subjects design to allow for meaningful assessment of the effects of cannabis on arterial stiffness. Similar to pulse wave velocity, flow-mediated dilation may vary substantially between and within subjects, with values as high as 20% reported in healthy individuals. This design is further warranted due to the choice of secondary endpoints. Exercise performance, and the accompanying physiological responses, are highly dependent on numerous factors that are likely to vary between individuals. Such factors include weight, fitness level, and familiarity with cycling. This further warrants the need for a within subject design, as these variables would have to be

matched if using parallel groups. Even if groups were matched, there is a strong likelihood that significant variability would exist in performance metrics.

The proposed study does not employ a placebo-control or a double-blind design. This is a consequence of the challenge owed to masking the device used to inhale cannabis in phase I. Vaporization and smoking are distinct methods of cannabis inhalation, and as such different devices must be used, making blinding difficult. A single-blind design will be utilized in phase II, in that participants will not be aware of the strain of cannabis they are consuming. Although collection will not be double-blind, investigators will be blind to condition during data analysis.

Randomization of the order of experimental visits in each phase will occur to combat improvement in performance as a result of better of pacing strategies, or improvements in fitness. Randomization will be performed using a randomization software ([www.random.org](http://www.random.org)). The order in which visits will occur will be individualized to each participant.

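### The exercise-only control is always Visit 1, outside the randomised order, so comparing cannabis-plus-exercise with exercise alone is confounded with bout order and the plan does not say so

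*Protocol*

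**What the plan says.** **Order.** Protocol 4.2 says that randomising the experimental visits "will occur to combat improvement in performance as a result of better of pacing strategies, or improvements in fitness". Section 4.1 defines experimental visits as 2 to 9, all with cannabis. The Schedule of Activities (1.3) footnote states "Visits 2-5 and 6-9 will occur in a randomized order, which will be individualized for each participant", and 6.3 adds "Each study visit will be assigned a number from 1-4". The exercise control is Visit 1, Day 7. The Schedule marks the 20-minute bout at Visits 1, 3, 5, 7 and 9, so only Visit 1 has a bout without cannabis.

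**Use of the control.** The secondary objective (Protocol 3) is the effect of prior cannabis on exercise performance. Secondary hypotheses 6 and 7 (Protocol 9.1, SAP 1) predict lower work and average power after every form of cannabis. Protocol 9.4.1 and 9.4.3 and SAP 4.1 and 4.3 plan repeated-measures one-way ANOVA and paired t-tests, with no period or bout term.

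**Shared control.** Protocol 4.1: "Each phase of the study will require participants to complete an introductory and control visit". The Schedule footnote says of people who join at Phase II without having done Phase I that "they will be required to complete the introductory and exercise control visits". The Synopsis says "participant duration of this study will be either 6 weeks, or 10 weeks".

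**Echocardiography.** Protocol 8.1 places the control-visit echo before exercise and the cannabis-visit echo after consumption. Protocol 4.1 says "Primary endpoints will be examined pre- and post-consumption each visit". Protocol 9.4.2 and SAP 4.2 have primary endpoints repeated after each intervention. The Schedule marks ordinary echo at Visits 1 to 9 without timing, and "Stress Echocardiography" at Visits 2, 4, 6 and 8 only.

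**The concern.** The plan identifies an order effect, randomises to deal with it, and leaves the key comparator outside the randomisation. A reader of 4.2 would think practice had been handled. For hypotheses 6 and 7 it has not: any change between the first and later bouts is added to the estimated cannabis effect. A practice gain would hide a real fall in work or power, or appear as an improvement. Fatigue or detraining would act the other way. More participants would not remove the bias.

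The echo item is separate and concerns primary endpoints. Protocol 9.4.1 and SAP 4.1 list exercise alone as a treatment level, and primary hypothesis 3 predicts an exercise-alone result for ejection fraction. The assessment section names no echo after exercise at the control visit that could supply it.

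**Working it through.** **1. The plan's own figure.** Protocol 9.2 requires 15 participants for power 0.8 at alpha 0.05. Its strain figures are -18.3 ± 1.2 and -17.0 ± 1.9. The pre-post correlation is not given; assume 0.5.

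- SD of the difference = √(1.2² + 1.9² − 2·0.5·1.2·1.9) = √2.77 = 1.664
- Standardised change = 1.3/1.664 = 0.781
- Exact two-sided paired t-test: power 0.803 at n=15

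The figure reproduces under that assumption (n=26 at correlation 0, n=11 at 0.7). It was set for FMD, pulse wave velocity and strain, so the plan states no power for exercise endpoints. I use it only to set a scale: 0.778 SD of the paired difference is what n=15 detects with 80% power.

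**2. Where the bouts fall.** Over all 24 orders of a phase's four cannabis visits, the control is bout 1 every time and each Phase I cannabis-plus-exercise condition is bout 2 or 3. The mean lag is 2.5 − 1 = 1.5 bouts. For a continuing participant who reuses the control, the Phase II bouts are 4 and 5, a mean lag of 3.5.

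**3. Can a bout term rescue the contrast?** Take participant effects, three exercise conditions, the control at bout 1 and the other two at bouts 2 and 3 in both orders.

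| Model | Columns | Rank | Cannabis+exercise minus control | Between the two cannabis+exercise visits |
|---|---|---|---|---|
| Categorical bout | 6 | 5 | not estimable | estimable |
| Linear bout | 5 | 5 | estimable | estimable |

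The linear model works only by assuming that the step from bout 1 to bout 2 equals later steps. The data cannot test this.

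**4. Illustrative size.** The documents give no practice effect. Let g be an assumed mean gain from the control to the later bout, in SDs of the paired difference. With an unadjusted two-sided 5% test, the noncentrality is (effect + g)·√n.

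| g | n=15: reduction of 0.778 SD detected | n=20: same | n=15, no cannabis effect: false improvement | n=15, no cannabis effect: false reduction |
|---|---|---|---|---|
| 0 | 80% | 91% | 2.5% | 2.5% |
| 0.2 | 55% | 69% | 10.8% | 0.4% |
| 0.3 | 41% | 53% | 19.0% | 0.1% |
| 0.5 | 17% | 22% | 43.8% | <0.1% |

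Example, g=0.2: (−0.778 + 0.2)·√15 = −2.24, giving 0.549. By symmetry, a loss of the same size swaps the last two columns. As a cross-check, a simulated drift of 0.2 SD per bout (mean shift 1.5 × 0.2 = 0.3) gave 40%, in line with the 41% above.

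**5. Shared control.** Visits 0 to 9 make ten visits for both phases, and one phase alone makes six. With the footnote and the Synopsis durations, this points to one control for continuing participants; 4.1 asks for one per phase. Nominal mean gap from control to the cannabis visits: Phase I, (14+21+28+35)/4 − 7 = 17.5 days; Phase II with reuse, (42+49+56+63)/4 − 7 = 45.5 days.

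**6. Echo passages side by side.** Section 8.1 gives before exercise (control) and after consumption (cannabis visits). Section 4.1 wants before and after consumption. Section 9.4.2 wants after each intervention. Section 9.4.1 and hypothesis 3 need an exercise-alone value. These cannot all be followed as written. Whether echo follows exercise at cannabis-plus-exercise visits is also not stated.

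**The case against.** - *The Schedule shows openly that Visit 1 comes first.* True, but it discloses timing, not the consequence for inference.
- *Practice works against hypotheses 6 and 7, so it is conservative.* This stands in part: a practice gain would not manufacture the predicted reduction. It would mask one or yield a false improvement, and drift in the other direction cannot be excluded.
- *The size is unknown.* This stands. The percentages show sensitivity; they do not estimate what will happen.
- *The VO2 max test at Visit 0 gives prior exposure.* It is a different test, not the 20-minute bout, and is not described as familiarisation.
- *Some exercise hypotheses have a randomised test.* This stands. A reader might infer that hypotheses 6 to 10 all lack one. Items 8 and 9 concern high-THC cannabis, and Phase II randomises THC-plus-exercise against CBD-plus-exercise, though that contrast is relative to CBD, not to no cannabis.
- *Section 8.1 does not exclude a post-exercise echo.* This stands. A reader might infer that none will be taken at the control visit, but the text names only the earlier one, and 9.4.2 points the other way. It is a conflict between passages.

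**Conclusion.** The point holds and should be fixed. Contrasts of cannabis-plus-exercise with exercise alone are non-randomised and confounded with bout order. This covers secondary hypotheses 6 and 7, the attenuation clause of item 4, and items 8 to 10 where exercise alone is the comparator. The aliasing follows from the schedule and needs no assumption; the size does. At assumed gains of 0.2 to 0.5 SD the loss of detection is material, and it depends on an unadjusted paired t-test and a scale borrowed from the strain calculation.

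Two stronger readings are not supported. A reader might infer that the exercise comparisons as a whole are invalid. They are not: smoking against vaporising, and THC against CBD, are randomised in the exercise setting, one contrast per phase, because only two of the four randomised sessions include the bout. A reader might also take 45.5 days as the actual gap. It is the nominal figure: 5.3 reschedules visits after a positive urine THC test and 9.4.6 completes Phase I before Phase II, so the real gap may be longer.

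On echo, the finding is that the timing passages conflict and the exercise-alone cardiac level has no clearly planned post-exercise measurement.

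**What to change.** **1. Control contrasts.** Add to Protocol 9.4.3 and SAP 4.3, in substance:

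> *Contrasts with the exercise control visit on exercise endpoints are non-randomised, because that visit is always the first bout, and are confounded with bout order. Conclusions on the secondary objective and on hypotheses 6 and 7 are qualified accordingly. A sensitivity analysis with a linear bout term will be reported; it assumes that the first-to-second step equals later steps. In each phase the randomised exercise contrast is the one between its two cannabis-plus-exercise visits. Hypotheses 8 and 9 can be tested in Phase II by THC-plus-exercise against CBD-plus-exercise.*

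The cost is wording and one extra model, plus accepting a weaker claim on the secondary objective.

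*Alternative, if a randomised test of hypotheses 6 and 7 is wanted:* put the control into the random order, five positions per phase, and amend 1.3, 8.1 and the Synopsis durations. The mean lag becomes zero. The costs are a new allocation list, changed visit windows and, for a continuing participant, an eleventh visit. Each exercise session is then first in 40 of 120 orders, so without a bout term a first-bout deficit g adds (2/3)g² to the variance of the other exercise contrasts: 2.7%, 6.0% and 16.7% for 0.2, 0.3 and 0.5 SD.

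**2. Shared control.** Reconcile 4.1 with the Schedule footnote and the Synopsis. If continuing participants reuse the Phase I control, report the actual gap. Wording only.

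**3. Echo (separate item).** Reconcile 8.1 with 4.1, 9.4.1, 9.4.2, SAP 4.1 and 4.2, primary hypothesis 3 and the stress-echo row, so that timing relative to exercise is the same at all exercise visits. If no post-exercise echo is taken at the control visit, remove the exercise-alone cardiac contrasts from Protocol 9.1 and 9.4.1 and SAP 1 and 4.1. Removal is wording only; otherwise the cost is a post-exercise echo at the control visit, and at cannabis-plus-exercise visits if none was intended there.
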